ANC	Absolute neutrophil count
APC	Antigen presenting cell
APTT	Activated partial thromboplastin time
AST	Aspartate transaminase
ATP	Adenosine triphosphate
C	Cycle
CD	Cluster differentiation
CI	Chief Investigator
CNS	Central nervous system
CR	Complete response
CRFs	Case Report Forms
CT	Computerised tomography
CTA	Clinical Trial Authorisation
CTCAE	Common Toxicity Criteria for Adverse Events
ctDNA	Circulating tumour deoxyribonucleic acid
CTLA-4	Cytotoxic T-lymphocyte antigen-4
D	Day
DCR	Disease control rate
DLT	Dose limiting toxicity
DO.R	Duration of response
DSUR	Development Safety Update Report
ECI	Event of clinical interest
ECOG	Eastern Cooperative Oncology Group
EGFR	Epidermal growth factor receptor gene
FDA	Food and Drug Administration
FEV ₁	Forced expiratory volume in 1 second
FVC	Forced vital capacity
GCP	Good Clinical Practice
GFR	Glomerular filtration rate
Gy	Gray
HIV	Human immunodeficiency virus
HMGB1	High-mobility group protein B1
HR	Hazard ratio
i.v.	Intravenous
IB	Investigator's Brochure
ID	Identification
IEC	Independent Ethics Committee
IL	Interleukin
IMP	Investigational Medicinal Product
IR	Ionising radiation
irAE	Immune-related adverse events
IRD	Institutional Review Board
irECI	Immune-related events of clinical interest

irRC	Immune-related response criteria
ITIM	Immunoreceptor tyrosine-based inhibition motif
ITSM	Immunoreceptor tyrosine-based switch motif
Kg	Kilogram
L	Litre
MAD	Maximum administered dose
mg	Milligram
MHC	Major histocompatibility complex
MHRA	Medicines and Healthcare Products Regulations
mmol	Millimoles
MRC	Medical Research Council
MSD	Merck Sharp & Dohme
MTD	Maximum tolerated dose
NCI	National Cancer Institute
NCRI CTRad	National Cancer Research Institute Clinical and Translational Radiotherapy Research Working Group
NK	Natural killer cells
ORR	Overall response rate
OS	Overall survival
PD	Progressive disease
PD-1	Programmed cell death protein 1
PD-L1	Programmed death ligand-1
PD-L2	Programmed death ligand-2
PFS	Progression free survival
PI	Principal Investigator
PR	Partial response
PT	Prothrombin time
QA	Quality Assurance
QC	Quality Control
RDSU	Research & Development Statistical Unit
REC	Research Ethics Committee
RECIST	Response evaluation criteria in solid tumours
RM-CTU	Royal Marsden Clinical Trials Unit
RP2D	Recommended phase 2 dose
SAE	Serious adverse events
SBRT	Stereotactic body radiotherapy
SD	Stable disease
SGOT	Serum glutamic oxaloacetic transaminase
SGPT	Serum glutamic pyruvic transaminase

1 TRIAL SUMMARY

Abbreviated Title	Pembrolizumab and stereotactic radiotherapy
Trial Phase	Phase I
Clinical Indication	Advanced malignant pleural mesothelioma
Trial Type	Interventional
Type of control	Single arm study: No treatment control
Route of administration	Intravenous Pembrolizumab and External Beam Stereotactic Body Radiotherapy (SBRT)
Trial Blinding	Unblinded, open label, phase I study, with a subsequent cohort expansion phase.
Treatment Groups	
Part A – Initial safety cohort
 
 Patients will receive an initial dose of pembrolizumab in week 1 dosed at 200 mg. They will then receive SBRT dosed at 30 Gy in 3 fractions (#) alternate days in week 3. Treatment with pembrolizumab will be continued dosed at 200 mg given every 3 weeks. If dose limiting toxicities are seen the study will be terminated. 
Part B – Expansion cohort.
 
An additional 12 patients will be recruited for this cohort. Patients will receive an initial dose of pembrolizumab at 200 mg in week 1. This will be followed in by SBRT dosed at 30 Gy in 3 fractions (#) alternate days in week 3. Treatment with pembrolizumab will be continued dosed at 200 mg given every 3 weeks.

Number of trial patients	Up to 18 patients may be recruited to the study – 6 patients will be recruited in part A. The expansion phase will recruit a further 12 patients in part B.
Duration of trial	24 months
Participation	Until progression, intolerance or withdrawal from the trial.
Study Objectives	
Primary
 
 To assess the safety and tolerability of 30 Gy in 3 fractions over a week delivered via SBRT in MPM in combination with pembrolizumab. 
Secondary
 
 To describe the safety profile of SBRT in MPM in combination with pembrolizumab. To assess clinical benefit by calculating the overall responses rates (ORR) and disease control rate (DCR). To assess responses rates in epithelioid versus sarcomatoid histological subtypes of MPM. To assess response rates in relation to tumour PD-1/PD-L1 expression. To assess progression free survival (PFS) and overall survival (OS). 
Exploratory
 
 To identify biomarkers that correlate with immunological response to therapy. To analyse peripheral blood samples for ctDNA.
Study Endpoints	
Primary
 
 To confirm that 30 Gy in 3 fractions over 1 week is a safe dose for phase 2 trials (RP2D) of SBRT in MPM combined with pembrolizumab.

	
Secondary
 
 1. To assess the rates of acute toxicity (defined as up to 12 weeks after the last fraction of SBRT) using CTC AE v5.0. 2. To assess the rates of late toxicity (defined as from 12 weeks after last fraction of SBRT in MPM until 28 days after the last dose of pembrolizumab) using CTC AE v5.0. 3. To calculate the ORR and DCR using mRECIST and RESIST 1.1. 4. To calculate the ORR and DCR in epithelioid versus sarcomatoid histological subtype using mRECIST and RESIST 1.1. 5. To assess the frequency of PD-1/PD-L1 expression distribution in responders and non-responders. 6. To measure the PFS and OS at 6 and 12 months. 
Exploratory
 
 1. To characterize tumour infiltrating lymphocytes and tumour antigens in the tumour biopsies. These immunohistochemistry analyses will include, but not necessarily be limited to, the following markers: CD4, CD8, FOXP3, PD-1, PD-L1, and PD-L2. 2. To assess for levels of ctDNA pre- and post- SBRT.

Summary of Main Inclusion Criteria
 
Female of childbearing potential is defined as women following menarche and until becoming post-menopausal unless permanently sterile. Permanent sterilisation methods include hysterectomy, bilateral salpingectomy and bilateral oophorectomy.
	
 1. Patients should be ≥ 18 years old on the day of signing the informed consent. 2. Patients must have a histological or cytological diagnosis of MPM. 3. Patients should have non-radically treatable MPM (i.e. not being considered for extrapleural pneumonectomy or pleurectomy and decortication). 4. Patients must have measurable disease as assessed by mRECIST. 5. Patients must have had disease progression or be intolerant of standard first-line palliative chemotherapy for MPM. Patients who have declined first-line palliative chemotherapy must have been suitable for platinum-doublet combination chemotherapy. 6. Patient should have an ECOG performance status 0-1 7. Patients should be able to tolerate a course of SBRT as assessed by the investigator. 8. Patients should have pleural-based disease, away from critical structures, suitable for treatment to part of lesion with SBRT. 9. Patients must have adequate organ function including MRC dyspnoea score <3 and adequate baseline lung function tests, with an FEV₁ $>0.8L$ or $>30\%$ of predicted and a TLCO $>30\%$ 10. Demonstrate adequate organ function as detailed in Table 2 (based on bloods within 10 days of C1D1). 11. Have provided tissue from an archival tissue sample or newly obtained tissue sample. 12. Female patient of childbearing potential¹⁰ should have a negative serum pregnancy within 72 hours prior to receiving the first dose of study medication (C1D1). 13. Female patients of childbearing potential should be willing to use highly effective methods of contraception for the course of the study through 120 days after the last dose of study medication. 14. Male patients should agree to use an adequate method of contraception starting with the first dose of study therapy through 120 days after the last dose of study therapy. 15. Be willing to provide informed consent for the trial.

Summary of Main Exclusion Criteria	
 1. Patients who have taken any investigational medicinal product or have used an investigational device within 4 weeks of the first dose of pembrolizumab. Patients are allowed to participate in additional observational studies. 2. Patients who have received prior chemotherapy, targeted small molecule therapy or radiotherapy within 4 weeks prior to the first dose of pembrolizumab. 3. Patients with a diagnosis of immunodeficiency or be receiving systemic steroid therapy (>7.5 mg of prednisone / >1 mg of dexamethasone or their equivalent dose) or any other form of immunosuppressive therapy within 7 days prior to the first dose. 4. Patients with evidence of active autoimmune disease requiring systemic treatment within the past 3 months or a documented history of clinically severe autoimmune disease, or a syndrome that requires systemic steroids or immunosuppressive agents or an autoimmune disease that is currently quiescent off any treatment, but deemed at risk of a significant flare if treated on this protocol. 5. Patients who have received prior therapy with an anti-PD-1, anti-PD-L1, anti-PD-L2, anti-CD137, or anti-Cytotoxic T-lymphocyte-associated antigen-4 (CTLA-4) antibody (including ipilimumab or any other antibody or drug specifically targeting T-cell co-stimulation or checkpoint pathways). 6. Patients with evidence of active central nervous system (CNS) metastases and/or carcinomatous meningitis. Patients with previously treated brain metastases may participate provided the brain metastases are stable and there is no evidence of new or enlarging brain metastases. 7. Patients who have had previous radiotherapy to the thorax or other neighbouring region that would preclude the safe administration of SBRT for MPM. 8. Patients with evidence of interstitial lung disease, or history of pneumonitis (including non-infectious pneumonitis) that required steroids, or current pneumonitis (including non-infectious pneumonitis). 9. Patients with evidence of additional malignancy that is progressing or requires active treatment. 10. Patients with a history or current evidence of any condition, therapy, or laboratory abnormality that might confound trial results, interfere with the patient's participation or is not in the best interest of the patient. 11. Patients with psychiatric or substance abuse disorders that would interfere with patients participation. 12. Patients who are pregnant / breastfeeding or expecting to conceive within the duration of the trial, starting with the screening visit through 120 days after the last dose. 13. Patients with a history of HIV, HIV 1/2 antibodies, Hepatitis B or Hepatitis C. 14. Patients with any active infection requiring systemic treatment 15. Patients who have received a live vaccine within 30 days prior to the first dose of trial treatment. 16. Patients with known hypersensitivity to the active substance pembrolizumab or to any of the excipients listed in the IB.
Treatment / Main Study Procedures	During the initial phase, patients will receive a dose of pembrolizumab during week 1 dosed at 200 mg, followed by SBRT in week 3 of 30 Gy in 3 fractions. Treatment with pembrolizumab will be continued dosed at 200 mg

every 3 weeks. Subsequently, there will be an expansion cohort phase where patients will receive a dose of pembrolizumab at 200 mg in week 1, followed by SBRT delivered as in the initial cohort. Treatment with pembrolizumab will be continued dosed at 200 mg given every 3 weeks.

Patients will undergo clinical assessment on the day of each administration of pembrolizumab and during the week of SBRT. Patients will continue on maintenance until disease progression, unacceptable adverse events, discontinuation of study medication for any other reason or withdrawal from the trial. Treatment beyond disease progression may be considered if there is deemed to be clinical benefit. All clinical assessments should be completed and reviewed before the administration of the next dose.

After the end of treatment each patient will be required to attend a safety follow up visit at 30 days or before the initiation of a new cancer treatment, whichever comes first. Patients who discontinue for reasons other than disease progression will be followed-up every 9 weeks for disease status until progression, initiating a new anti-cancer treatment, withdrawing consent, or becoming lost to follow-up. Once a patient has suffered disease progression or initiated a new cancer treatment they will be followed up every 12 weeks to determine their disease status. This will be done by reviewing their medical notes and/or contacting the patient or GP directly. Patients will remain on this follow-up until death, withdrawal of consent or the end of the study.

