6.3 Clinical Procedures/Assessments

6.3.1 PD-L1 Assessment

To participate in the trial patients need available tissue of a tumour lesion not previously irradiated (tumours progressing in a prior site of radiation are allowed) for PD-L1 characterisation. This specimen will be evaluated at a central laboratory for expression status of PD-L1 by the PD-L1 IHC 22C3 pharmDx (Dako). If no tissue is available, then following informed consent they should undergo a biopsy of a tumour lesion for biomarker analysis. NOTE: Patients participating in this trial will be unselected for their PD-L1 status.

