6.3.13 Tumour Biopsies and Research Blood Samples

For patients without archived samples, tumour biopsies will be obtained during the screening period. If the patient consents optional research blood samples will be obtained at C1D1, C2D1, C5D1 and at the end of study visit (Table 3). Tumour and blood samples from this study may undergo proteomic, genomic and transcriptional analyses. Additional research may evaluate factors important for predicting responsiveness or resistance to pembrolizumab therapy and radiotherapy. Assays may include, but are not limited to:

- **Characterisation of TILs and tumour antigens**

Immunohistochemistry (IHC) will be used to assess the number and composition of immune infiltrates in order to define the immune cell subsets present within formalin-fixed, paraffin embedded (FFPE) tumour tissue before and after exposure to therapy. These IHC analyses will include, but not necessarily be limited to, the following: CD4, CD8, FOXP3, PD-1, PD-L1, and PD-L2.

- **ctDNA & CTCs**

Research blood samples will be analysed for ctDNA and CTCs. Analysis of CTCs will include, but not necessarily limited to the following, the diagnostic performance of PD-L1 testing will be assessed in CTC compared with IHC, correlation with response and disease progression.

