9.1.2 Secondary Endpoints

Acute and late toxicity data will be tabulated by type, grade and dose level with the number, proportions and frequencies of grades 1-4 and grade 3-4 grades reported. The duration of clinical benefit assessed by overall response rate (ORR) defined as complete response (CR) or partial response (PR) and disease control rate (DCR) defined as CR, PR or stable disease (SD) using modified RECIST (Appendix 6) and RECIST 1.1 will be calculated as a proportion of total treated with a 95% confidence interval. Response rates (ORR and DCR), will be calculated as proportions for all patients and in the epithelioid and sarcomatoid histological sub-type giving associated 95% confidence intervals. Any difference in response rates (for ORR and for DCR) between the two sub-types will be compared using a chi squared or Fisher's exact test as appropriate. These will be evaluated for Part A and Part B and for overall. PD-L1 staining is referred to as tumour proportion score, reported as a percentage from 0–100%. It is classed as weakly positive (1 – 49%); strongly positive if >50%; and negative if <1%. The effect of PD-L1 expression on response rates will be measured using the proportion

of patients recorded to be weakly positive, strongly positive or negative and tested using a Chi Squared or Fisher's exact test for proportions on expression level between responders and non-responders. PFS will be measured from the start of radiotherapy until radiological or clinical evidence of progression or death and will be censored at date of last follow-up for surviving patients. OS will be measured from the start of radiotherapy until death and will be censored at date of last follow-up for surviving patients. Duration of response (DOR) will be measured from the date of first response until radiological or clinical evidence of progression or death and will be censored at date of last follow-up for surviving patients. Median PFS, OS and DOR will be calculated using Kaplan-Meier methods giving associated 95% confidence intervals, respectively. PFS, OS and DOR rates at 6 and 12 months will be presented with associated 95% confidence intervals. PFS, OS and DOR will be assessed for overall i.e. Part A and Part B combined. Unless otherwise stated, all secondary endpoints will be analysed for Part A, Part B and overall.

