9.1.3 Exploratory Endpoints

Exploratory endpoints will be presented in a descriptive fashion. We will:

- Describe the patterns of TILs and tumour antigens in archival tumour biopsies. These immunohistochemistry analyses will include, but not necessarily be limited to, the following markers: CD4, CD8, FOXP3, PD-1, PD-L1, and PD-L2.
- Blood will be analysed for ctDNA pre- and post- SBRT.

Exploratory endpoints will be analysed for Part A, Part B and overall.

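### The PD-L1 secondary endpoint reports expression classes among responders and non-responders, while its objective asks for response rates; no ORR or DCR by PD-L1 class is planned

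*Protocol*

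**What the plan says.** The secondary objective in section 1 (Trial Summary), repeated in 3.1.2, is "To assess response rates in relation to tumour PD-1/PD-L1 expression". The corresponding endpoint, in section 1 and again in 3.2.2, is "To assess the frequency of PD-1/PD-L1 expression distribution in responders and non-responders".

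The analysis is in section 9.1.2. It opens "The effect of PD-L1 expression on response rates will be measured using the proportion", then names three PD-L1 classes, and for the comparison specifies "Fisher's exact test for proportions on expression level between responders and non-responders", with a chi-squared test as the alternative. The three classes (negative, weakly positive, strongly positive) are cut points of the PD-L1 tumour proportion score. Earlier in the same section, ORR and DCR are to be calculated within the epithelioid and sarcomatoid subtypes, each with a 95% confidence interval, and then compared by a chi-squared or Fisher test.

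On PD-1, the dedicated tissue assay in 6.3.1 and the assessment scheduled in Table 3 are for PD-L1 only. PD-1 appears in the marker panel of 6.3.13: "These IHC analyses will include, but not necessarily be limited to, the following: CD4, CD8, FOXP3, PD-1, PD-L1, and PD-L2". The same panel is listed under the exploratory endpoints in 3.2.3 and 9.1.3, where "Exploratory endpoints will be presented in a descriptive fashion".

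**The concern.** The objective conditions on expression: among patients in a given PD-L1 class, what fraction respond? The endpoint and analysis condition on response: among responders, and among non-responders, what fraction fall in each class? Section 9.1.2 names the first quantity as its target and then specifies the second as its measure.

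The reader of the trial report will want the response rate in PD-L1-negative, weakly positive and strongly positive patients, with its uncertainty. In at most 18 patients a p-value says little about that, and the planned percentages cannot be read as response rates. The histology analysis has a parallel objective and does get rates with intervals.

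A smaller matter is that PD-1 is named in the secondary objective and endpoint, but section 9.1.2 contains no PD-1 scoring, classes or test.

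**Working it through.** The protocol states no sample size, power or effect size for this endpoint, so there is no figure to reproduce. The check uses illustrative tables at the maximum of 18 treated patients (section 4.2). All cell counts are assumptions, with 5 responders and 13 non-responders throughout.

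**Quantities**
- Asked for by the objective: responders in a class ÷ all patients in that class.
- Reported under the plan: patients of a class among responders ÷ all responders, and the same for non-responders.

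**Two tables, with PD-L1 collapsed to positive or negative**

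| | Table 1 | Table 2 |
|---|---|---|
| Positive: responders / patients | 4/8 | 4/14 |
| Negative: responders / patients | 1/10 | 1/4 |
| Response rate, positive vs negative | 50% vs 10% | 29% vs 25% |
| Share positive, responders | 4/5 = 80% | 4/5 = 80% |
| Share positive, non-responders | 4/13 = 31% | 10/13 = 77% |
| Odds ratio | (4×9)/(4×1) = 9.0 | (4×3)/(10×1) = 1.2 |
| Fisher p, two-sided | 0.118 | 1.0 |

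The share of responders who are positive is 80% in both tables, but the response rate among positives is 50% in one and 29% in the other. Transposing each table leaves the Fisher p-value and the odds ratio unchanged. For Table 1 the uncorrected chi-squared p-value is 0.060 in both directions.

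**Three classes, as the plan uses.** Assume responses in 1/10 negative, 2/5 weakly positive and 2/3 strongly positive patients. The objective's quantities are 10%, 40% and 67%. The plan reports 20%, 40% and 40% of responders (1/5, 2/5, 2/5) against 69%, 23% and 8% of non-responders (9/13, 3/13, 1/13). The chi-squared p-value is 0.122 in both directions.

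**Precision of the proposed estimate (exact, Clopper-Pearson).** 4/8 gives 16% to 84%, and 1/10 gives 0.3% to 45%. A class of three patients with one response gives about 1% to 91%.

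**PD-1, place by place**
- Named in the secondary objective (1, 3.1.2) and endpoint (1, 3.2.2).
- Absent from 6.3.1, from the PD-L1 row of Table 3 and from the classes and test in 9.1.2.
- Present in the exploratory panel (3.2.3, 6.3.13, 9.1.3), which is descriptive.

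**The case against.** A reader might infer that the analysis does not answer its objective at all. The documents do not support that. The objective asks for response rates in relation to expression, section 9.1.2 tests that relation, and the test and odds ratio are the same whichever way the table is percentaged. If all cell counts are published, response rates by class can be recovered.

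A reader might also infer that the planned figures drift with the prevalence of PD-L1 positivity and so carry no information on effect. Looking at responders alone invites this. With assumed response rates of 50% and 10%, their share positive is p×0.5 / (p×0.5 + (1−p)×0.1), or 57%, 77% and 81% at the prevalences of 20.7%, 40% and 45.2% quoted in sections 2.2.4 and 2.2.6.2. But the plan also reports non-responders, whose share is p×0.5 / (p×0.5 + (1−p)×0.9), or about 13%, 27% and 31%. The odds ratio from the pair is 9.0 in all three cases. Those prevalences also come from different antibodies and definitions of positivity, so they are no more than a rough range.

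It can further be said that section 9.1 already promises frequencies, proportions and intervals where appropriate, that table layout belongs in an analysis plan not shown here, that describing a biomarker by response status is legitimate in phase 1, and that no decision rests on this endpoint because the primary endpoint is DLT. These points limit the weight of the concern. They do not remove it: the protocol itself fixes the estimate in the summary, in 3.2.2 and in 9.1.2, and it is not the one the objective asks for.

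On PD-1, it would be too strong to say that it cannot be reported. Staining for it is already foreseen, and the paired label may be shorthand for the pathway.

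**Conclusion.** The point holds as a mismatch between objective and pre-specified estimate. The association is validly tested. What is missing is a planned ORR and DCR, with intervals, by PD-L1 class. The size is shown by the illustration: one and the same planned figure, 80% of responders positive, is compatible with a response rate among positives of 50% or 29%, and only the non-responder column or the cell counts tell these apart. This rests on assumed counts. That the two kinds of proportion differ follows from their definitions and does not depend on those counts.

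The consequence is confined to a secondary endpoint of a single-arm phase 1 trial, and the change is worth making because it is cheap. It will not bring precision: with at most 18 patients in three classes, the intervals will be wide.

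The PD-1 point is a minor inconsistency of level. The marker is named as secondary but handled only as exploratory.

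**What to change.** 1. In sections 1, 3.2.2 and 9.1.2, define the endpoint as ORR and DCR with exact 95% confidence intervals within each PD-L1 class, in treated patients with a PD-L1 result. This matches the form already used for histology.
2. Keep the Fisher or chi-squared test as supportive.
3. Reconcile PD-1 in one of two ways. Either move it out of the secondary objective and endpoint (sections 1, 3.1.2, 3.2.2) and leave it with the exploratory panel, or carry the already planned PD-1 immunohistochemistry into 9.1.2 with its scoring and analysis.

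The PD-L1 change costs wording in three sections and a few rows in one table, with no new data, assay or patients. Moving PD-1 to exploratory is also wording only. Keeping it at secondary level needs a scoring rule and an analysis to be written for staining that is already planned.
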